## **Secondary Aims**

### **Secondary Aim 1:**

To assess the duration of the local analgesia (determined by pinprick and cold) in all four quadrants with liposomal bupivacaine, plain bupivacaine, and placebo after major abdominal surgery.

Hypothesis. Abdominal wall analgesia from four-quadrant TAP blocks with single-shot liposomal bupivacaine lasts longer after major abdominal surgery than the same blocks with plain bupivacaine or placebo. Our major outcome will be time from end of the block until abdominal wall sensation with both ice and pinprick recovers in at least six of eight designated locations. Two sequential evaluations will be needed to be negative and first negative time point will be accepted as the return of sensation.

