**Placebo group;** patients will receive total of 80 ml of normal saline, injected 20 ml in each of the four-quadrant sites.

General anesthesia will be induced using propofol or etomidate, fentanyl, and rocuronium to facilitate intubation. Anesthesia will be maintained with sevoflurane or isoflurane, along with opioids and muscle relaxants as clinically indicated. However, intraoperative analgesic use will be limited to fentanyl, a short-acting opioid.

Postoperatively, patients will be given intravenous patient-controlled analgesia and nurses will be free to give additional opioid as clinically indicated. Hydromorphone will be the default drug, but fentanyl will be substituted if necessary. Clinicians blinded to trial drug will adjust analgesic management as necessary in an effort to keep verbal response pain scores (details below) <4 points on a 0-10 scale, with 10 being worst pain. When patients no longer need PCA, they will be switched to as-needed hydromorphone or fentanyl.

A single dose of dexamethasone (4-8 mg) will be given to all patients for PONV prophylaxis, and inhaled steroids will be permitted as necessary to treat reactive airway disease. The use of non-steroidal anti-inflammatory drugs and gabapentinoids will be allowed as part of the ERAS approach (enhanced recovery after surgery) according to hospital's clinical practice. Other opioid-sparing medications such as ketamine and lidocaine patches will not be permitted through the initial 72 postoperative hours. Vital

signs and patient activity will be continuously monitored and recorded with a wireless monitor (ViSi mobile, Sotera Wireless, San Diego, CA). Monitoring will be started about 30 minutes after arrival in the postanesthesia care unit and continued for 72 hours while patients remained hospitalized. Clinicians will be blinded to continuous monitoring data; clinical decisions therefore will be guided by routine intermittent vital signs which were typically obtained at 4-hour intervals.

Patients will be allowed to receive prophylactic anti-emetic (first choice ondansetron) intraoperatively based on the risk assessment for nausea and vomiting. Postoperative anti-emetics for symptomatic treatment will also be allowed; again ondansetron will be the first choice.

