nursing floor at one hour intervals. Subsequently, assessments will be performed at 2 hourly intervals (x3) then at 12 hours postop (defined as patient leaving the OR), 18 hours postop, 24 hours postop, 30, 36 hours postop, 48 hours postop, 60 hours postop, 72 hours postop (when patients are not sleeping). Testing will continue until abdominal wall sensation returns or 72 hours have elapsed since surgery. We will consider sensation recovered when patients feel both ice and pinprick in at least 6 of the 8 designated test locations. If the TAP block did not initially cover all eight locations, sensation will be considered recovered when patients sense ice and pinprick at  $\geq 75\%$  of the covered points (i.e., 5/7, 5/6, 4/5, 3/4, 3/3, etc.). Two sequential evaluations will be needed to be negative and first negative time will be accepted as the return of sensation.

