## **Secondary Outcomes.**

*Time to return of sensation.* We will compare the 3 randomized groups on the time to detection of return of sensation (see above; i.e., when patients feels both ice and pinprick in at least 6 of the 8 designated test locations, or  $\geq 75\%$  of the covered points if the TAP block did not initially cover all eight locations) using a time-to event Kaplan-Meier analysis and log-rank test, and comparing patients on the estimated median time to return of sensation. If all patients do have return of sensation (as expected), the analysis will be equivalent to a Wilcoxon rank sum test, and so this test and the corresponding Hodges-Lehman estimator of median difference (CI) will be reported as a sensitivity analysis. The significance criterion for each of the 3 comparisons will be  $0.05/3 = 0.0167$  to control the type I error at 0.05 for the primary outcome.

*Pain score.* We will compare the 3 randomized groups on mean pain score over the first 72 hours using a linear mixed effects model in which we adjust for within-subject

correlation assuming an autoregressive correlation structure (or unstructured or other, whichever fits best; but making sure to also account for the differences in timing between the measurements) with fixed effects of treatment and categorical time. While we will assess the treatment-by-time interaction, main results will be reported collapsing over time regardless of a significant interaction.

*Opioid consumption 48-72 hours.* This will be analyzed using linear regression as with the primary outcomes.

[figure not shown]
Type I error will be controlled at 0.05 for secondary outcomes by using a significance criterion of  $0.05/3=0.017$  for each outcome.

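### The return-of-sensation rule lists 5/7 (71.4%) as meeting a 75% threshold, differs from the definition in Secondary Aim 1, and assigns no time to a patient with no covered point

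*Combined protocol and SAP*

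**What the plan says.** Three sections define the event for time to return of sensation.

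- **Secondary Aim 1 (section 2, Study Objectives)** defines the outcome as "time from end of the block until abdominal wall sensation with both ice and pinprick recovers in at least six of eight designated locations". It makes no exception for partial coverage.
- **Secondary Outcome 1 (section 3.E, Measurements)** starts from the same base rule: "We will consider sensation recovered when patients feel both ice and pinprick in at least 6 of the 8 designated test locations". It then adds a conditional rule: "If the TAP block did not initially cover all eight locations, sensation will be considered recovered when patients sense ice and pinprick at" 75% or more "of the covered points (i.e., 5/7, 5/6, 4/5, 3/4, 3/3, etc". For confirmation: "Two sequential evaluations will be needed to be negative and first negative time will be accepted as the return of sensation".
- **Secondary Outcomes (section 3.F, Data Analysis)** repeats the two-part rule, with at least 75% "of the covered points if the TAP block did not initially cover all eight locations", but without the fractions. It compares all three randomized groups by Kaplan-Meier and log-rank methods.

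Placebo is saline only (section 3.D): "patients will receive total of 80 ml of normal saline, injected 20 ml in each of the four-quadrant sites".

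**The concern.** The fractions are introduced as a restatement of the rule, not as loose examples, so an assessor or programmer may use them as the rule. One of them contradicts the percentage beside it. Two people working from the same sentence could date recovery differently in the same patient.

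There are two further gaps. Someone working from Secondary Aim 1 would apply 6 of 8 to everyone, while someone working from section 3.E or 3.F would apply 75% of covered points to partly covered patients. And the conditional rule, read literally, includes a patient with no covered point, for whom the fraction is 0/0. Little or no coverage is the expected state after a saline injection, and placebo enters two of the three pairwise comparisons.

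At stake is the event definition of a formally tested secondary outcome. The Economic Analysis paragraph in section 3.F also uses time to return of sensation as the denominator of the cost-effectiveness ratio.

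**Working it through.** **Inputs.** The 6-of-8 base rule, the 75% threshold and the fractions come from Secondary Outcome 1 in section 3.E. The unconditional 6-of-8 rule comes from Secondary Aim 1. The test schedule is in section 3.E.

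**Step 1: reproduce the list.** For k covered points, the smallest count meeting 75% is 0.75 × k rounded up. For comparison, if every uncovered point is felt (an assumption), 6 of 8 requires 6 − (8 − k) = k − 2 covered points, or zero if that is negative.

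| Covered points k | 0.75 × k | Smallest count at 75% or more | Listed | Needed under 6 of 8 |
|---|---|---|---|---|
| 8 | 6.00 | 6 (75.0%) | 6 (base rule) | 6 |
| 7 | 5.25 | 6 (85.7%) | 5 (71.4%) | 5 |
| 6 | 4.50 | 5 (83.3%) | 5 | 4 |
| 5 | 3.75 | 4 (80.0%) | 4 | 3 |
| 4 | 3.00 | 3 (75.0%) | 3 | 2 |
| 3 | 2.25 | 3 (100%) | 3 | 1 |
| 2 | 1.50 | 2 (100%) | none | 0 |
| 1 | 0.75 | 1 (100%) | none | 0 |
| 0 | 0 | 0/0, undefined | none | 0 |

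The threshold reproduces every listed count except 5/7.

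**Step 2: is there another rule behind the list?** Rounding 0.75 × k to the nearest integer gives 5/7 (5.25 to 5), but 2/3 for three points (2.25 to 2), where the list has 3/3. The 6-of-8 rule with uncovered points counted as felt gives 5/7, but then 4/6, 3/5, 2/4 and 1/3. None of the three rules tried reproduces the whole list.

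**Step 3: size of the 5/7 effect.** Reaching five points cannot come later than reaching six, so 5/7 dates recovery at the same test as 6/7 or earlier. When it is earlier, the shift is at least one test interval. The schedule has a first PACU/ICU test, two at 1 h intervals, three at 2 h intervals, then tests at 12, 18, 24, 30, 36, 48, 60 and 72 h. The step is therefore 1-2 h early, 6 h from 12 to 36 h and 12 h from 36 to 72 h. The gap just before the 12 h test depends on when the first test fell.

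As an illustration only, assume seven independent log-normal recovery times per patient, no return of numbness, and an approximate version of this schedule. None of these inputs is in the documents. The share of seven-point patients whose recorded test differs between 5/7 and 6/7 is:

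| Median recovery per point | Log-SD 0.3 | Log-SD 0.6 |
|---|---|---|
| 18 h | 40% | 64% |
| 48 h | 49% | 56% |

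These are shares of patients with exactly seven covered points, not of the trial.

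**Step 4: Secondary Aim 1 against sections 3.E and 3.F.** Compare the last column of the first table with the others. With the list as printed, the definitions coincide at seven points and differ for one to six. With 6/7 in place, they differ for one to seven. With one or two covered points, 6 of 8 is already met at the first postoperative test, while the covered-points rule waits for those points to return.

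**Step 5: zero coverage.** The covered-points rule is undefined (0/0). No section says whether such a patient is recovered at the first test, recovered at time zero, or left unscored.

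**The case against.** The strongest reply is that section 3.F, which governs the analysis, gives only the percentage. A derivation written from it would require 6/7, and the printed 5/7 would do no harm. That limits the consequence but does not remove it. Under section 3.E testing continues only until sensation returns, so an assessor who follows the list could stop before the sixth point is recorded.

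It can also be said that 5/7 may be what was meant and the percentage loose. That is possible. The contradiction still has to be settled, and 5/7 would need a threshold at or below 71.4%.

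A reader might infer that the 6-of-8 and 75% rules contradict each other inside sections 3.E and 3.F. The documents do not support this: the 75% rule is conditional there and replaces 6 of 8 under partial coverage, and the trailing etc. extends naturally to 2/2 and 1/1. The disagreement is with Secondary Aim 1. Zero coverage is an undefined case, not a clash between two answers.

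A reader might also infer that block duration will be mis-scored and the contrast between arms blurred. That is not shown. The documents give neither the number of patients with seven, few or no covered points nor their split by arm, so neither the size nor the direction of any effect on the comparison is known.

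**Conclusion.** The point holds as an inconsistency in an endpoint definition. That 5/7 (71.4%) fails a 75% threshold is plain arithmetic and needs no assumption. For a seven-point patient scored by the list, recovery falls at the same test or earlier than the threshold allows, by one test interval or more when it differs. Secondary Aim 1 disagrees with sections 3.E and 3.F for partly covered patients; the counts given for this assume that uncovered points are felt. The time assigned at zero coverage is missing, and this bears most on placebo.

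The reach is limited to Secondary Outcome 1 and the cost-effectiveness ratio that uses it. The opioid-consumption primary outcomes and the sample size do not depend on this definition.

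**What to change.** 1. In Secondary Outcome 1 (section 3.E), replace 5/7 with 6/7 and complete the list: 6/7, 5/6, 4/5, 3/4, 3/3, 2/2, 1/1. If 5/7 is intended, restate the threshold as at or below 71.4% and recheck the other counts against it.
2. State the same rule, including the partial-coverage condition, in Secondary Aim 1 (section 2), Secondary Outcome 1 (section 3.E) and Secondary Outcomes (section 3.F).
3. Prespecify, before unblinding, that a patient in any arm with no covered point at the first postoperative test is scored as recovered at that test, subject to the same two-sequential-evaluation confirmation. This also fixes the first postoperative test as the time when coverage is judged.

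A tempting shortcut is to score anyone who feels six or more of eight points at the first test as recovered then. It would create a step: with two covered points neither need return, but with three all three must. It would also leave Secondary Aim 1 unreconciled.

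The cost is one corrected fraction, matching text in three sections, and a check of the endpoint derivation program and assessor instructions. No added assessments are needed. For any patient whose testing already stopped on the 5/7 count, the 6/7 time may not be on record, and this should be checked before the rule is finalised.

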### ***Secondary outcome 2***

Pain Scores after surgery will be measured using a Verbal Response Scale (VRS). VRS is a scale from 0 to 10 where 0 signifies no pain and 10 signifies worst pain ever experienced. The VRS will be recorded at the same intervals as cold and pinprick sensation assessment described in *secondary outcome 2* above and thereafter at 4-hour intervals while patients are awake for 72 hours.

### ***Secondary outcome 3***

Opioid consumption will be measured as morphine equivalent in first between 48-72 hours.

To evaluate TAP blocks with liposomal bupivacaine, plain bupivacaine, and placebo on opioid consumption in 48 to 72 hours. Use of PCA and discontinuation will be recorded.

### ***Tertiary Outcome 1***

A composite of opioid-related side effect after surgery will be recorded for 72 hours. Components of the composite include nausea, vomiting, ileus, constipation, pruritus, itching, urinary retention, use of antiemetics or naloxone or antihistamines.

### ***Tertiary Outcome 2***

Patients will be asked to rate their satisfaction with pain management at using a 0-10 point scale at 72 hours or upon discharge if earlier.

### ***Tertiary Outcome 3***

Total cost of hospital care and specific care costs will be estimated from data in the electronic medical records database. Data obtained from electronic medical records will include: operation time, surgery type, intraoperative opioid consumption, postoperative opioid consumption in PACU and in ward, breakthrough pain medication requirements, pain scores in PACU and ward, requirement of oxygen in PACU and ward, pruritus, requirement of antihistaminic medications, requirement of naloxone, itching, ambulation time, flatus, ileus, bowel movements (first time documented), constipation, length of stay and any side effects or complications.

### ***Tertiary Outcome 4***

Pain Scores with movement after surgery will be measured using a Verbal Response Scale (VRS). The VRS will be recorded every 12 hours by asking patient to lift their legs up to 72 hours postop or until discharge, whichever is sooner. The patient will also be asked to report their VRS at rest prior to leg raise for reference.

### ***Tertiary Outcome 5.***

Patient's mobility will be obtained from VISI monitoring device for 72 hours/discharge surgery

## **F. Data Analysis**

Randomized groups will be compared for baseline balance using standard descriptive statistics and the standardized difference (difference in means or proportions divided by the pooled standard deviation).

**Primary Outcomes.** *Opioid consumption.* The following tests for superiority on opioid consumption will be conducted (see type I error control below): 1) 0-24 hours post-surgery: compare each of exparel and plain bupivacaine to placebo; and 2) 24-48 hours post-surgery: compare exparel to each of plain bupivacaine and placebo. Groups will be compared using linear regression on log-transformed morphine equivalents, with results reported as ratio of geometric means between each pair of interventions.

**Type I error control across Primary outcomes 1 and 2.** We will use a parallel gatekeeping procedure to control the type I error at 5% across the 2 primary outcomes. The 2 comparisons for the 0-24 hour period will constitute Set #1, and the 2 comparisons for the 24-48 hour period will constitute Set #2. Within each set we will use the Holm-Bonferroni (HB) multiple comparison procedure among the two comparisons. If either test in the first Set is significant (HB: significance criterion of 0.025 for smaller P-value and 0.05 for the larger), analysis will continue to Set #2. Otherwise, Set #2 will not be analyzed. If analysis proceeds to Set #2, the overall alpha for Set #2 will be  $0.05 \times$  proportion of significant tests in Set #1 (i.e., Set #2 alpha = either  $0.05 \times 1$  or  $0.05 \times .5 = 0.025$ ).

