### **3. Method and Study Design**

#### **A. Study Overview**

We propose a randomized double-blind trial comparing TAP blocks with liposomal bupivacaine, plain bupivacaine, and placebo in patients having elective abdominal surgery. The study will be performed at various Cleveland Clinic hospitals with IRB approval and written consent from patients. Study will be registered at ClinicalTrials.gov website before the first patient is enrolled.

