### **D. Protocol**

After eligibility is confirmed, patients will receive complete information about the study both verbally and in writing. Informed consent will be obtained from the patients prior to randomization and study-specific procedures.

Randomization will be based on computer-generated codes and use random-sized blocks. Allocations will be concealed until the morning of surgery where they will be provided by a web-based system. Randomization will be stratified by study site and chronic opioid use, defined by opioid use for more than 30 consecutive days within three preoperative months, at a daily dose of 15 mg or more of morphine or equivalent. Randomization will also be stratified according to anticipated type of surgery (open vs. laparoscopic-assisted). Clinicians doing the blocks will not be involved in data collection and all the evaluators will be blinded to group allocations.

All blocks will be performed preoperatively or after induction of anesthesia by attending anesthesiologists or regional anesthesia fellows who are experienced in TAP blocks. Premedication will be administered at the discretion of the attending anesthesiologist and standard monitors will be used. Patients will be given 1 g oral acetaminophen an hour before surgery, and an additional 500 mg every 6 hours for 72 hours after surgery starting with oral intake.

Patients will be randomly assigned to: 1) 4-quadrant TAP block with liposomal bupivacaine; 2) 4-quadrant TAP block with plain bupivacaine; or, 3) placebo (normal saline). An in-plane ultrasound will be guide TAP blocks. Two subcostal injections will be applied by placing the probe midline and then moving lateral along the subcostal margin identifying area between the rectus abdominis sheath and the transversus abdominis muscle. The lateral two TAP block injections will be applied in the midaxillary line between

the thoracic cage and iliac crest between external oblique and transversus abdominis muscles. Once the target area is positioned, the following injections will be given, based on randomization:

**Liposomal bupivacaine.** 40 ml of plain bupivacaine 0.25% will be mixed with 20 ml liposomal bupivacaine and 20 ml of saline. 20 ml of the mix will be injected at each location of the 4-quadrant TAP block.

**Plain bupivacaine group.** 50 ml of plain bupivacaine 0.5% will be combined with 30 ml of normal saline making a total of 80 ml. 20 ml will be injected at each location of the 4-quadrant TAP block.

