### **E. Measurements**

Demographic data to be obtained includes height (cm), weight (kg), age (yr), sex, (ASA) physical status, self-declared ethnicity, and the specific type of procedure will be recorded. Patients will be questioned about tobacco and alcohol use, and about illegal drug use. They will also be asked about their medical history including pulmonary disease, kidney disease, diabetes mellitus, neurological disease, chronic pain conditions, previous surgery or stent placement, and medications. Available preoperative laboratory tests and medication list will be recorded. Preoperative pain scores and opioid use will be recorded. Patients excluded for any reason including technical considerations or contraindications will be recorded.

All the procedures for the ultrasound guided TAP blocks will be recorded to the ultrasound and two blinded independent adjudicators will evaluate the success of the blocks. Blocks will be accepted as successful if 3 out of 4 locations were done correctly according to adjudicators.

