### **Tertiary Outcomes.**

Groups will be compared on the collapsed composite of opioid-related side effects in the first 72 hours after surgery using chi-square tests. Groups will be compared on satisfaction with pain management at using a 0-10 point scale at 72 hours, or upon discharge if earlier, using the Kruskal-Wallis test overall and Wilcoxon rank sum test between interventions.

**Economic Analysis.** Finally, if a treatment effect between the 2 local anesthetic TAP blocks is detected, we will conduct a cost-effectiveness analysis estimating the incremental cost-effectiveness ratio (ICER) as the mean difference in costs divided by the mean difference in the primary outcome of time to return of sensation [or an analogous ratio using summaries which best fit the distribution of the data]. Total cost of hospital care and specific care costs will be estimated from data in the electronic medical records database. Data obtained from electronic medical records will include: operation time, surgery type, intraoperative opioid consumption, postoperative opioid consumption in PACU and in ward, breakthrough pain medication requirements, pain scores in PACU and ward, requirement of oxygen in PACU and ward, pruritus, requirement of antihistaminic medications, requirement of naloxone, itching, ambulation time, flatus, ileus, bowel movements (first time documented), constipation, length of stay and any side effects or complications.

**Interim Analyses.** We will use a group sequential design to conduct interim analyses at each 25% of the planned enrollment to assess efficacy and futility of the intervention using a gamma spending function. Specifically, we will maintain the overall alpha level (monitoring efficacy) at 0.05 using gamma parameter of -4 [similar to O'Brien Fleming], and power at 90% (monitoring beta, type II error) using gamma parameter of 0 [more aggressive, similar to Pocock]. Under the alternative hypothesis (assuming a true 50% relative reduction in the primary outcome) the cumulative probability of crossing an efficacy (and futility in parentheses) boundary at the 1st through 4th analyses will be 0.09 (0.025), 0.39 (0.05), 0.75 (0.075) and 0.90 (0.10) as shown in **Figure 1**.

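### The stratification factors are not named in the opioid regressions or the pain model, so a small, low-cost gain in precision is not secured

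*Combined protocol and SAP*

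**What the plan says.** Section 3.D, on randomisation: "Randomization will be stratified by study site and chronic opioid use". The same paragraph adds the anticipated surgical approach, open or laparoscopic-assisted, as a third factor. Section 3.A does not give the number of sites: "The study will be performed at various" hospitals of one clinic system.

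Section 3.F, Primary Outcomes, gives the model for opioid use at 0-24 h and 24-48 h: "Groups will be compared using linear regression on log-transformed morphine equivalents, with results reported as ratio of geometric means between each pair of interventions". No covariate is named. For 48-72 h, Secondary Outcomes says: "This will be analyzed using linear regression as with the primary outcomes". The pain score is analysed by a linear mixed model "with fixed effects of treatment and categorical time". Section 3.F also plans to describe baseline balance by standardised differences, but it states no adjustment rule. No other section puts the stratification factors into a model.

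Two other places matter. Section 3.E says that "Preoperative pain scores and opioid use will be recorded", so further baseline covariates will be available. Section 3.F, Interim Analyses, says: "We will use a group sequential design to conduct interim analyses at each 25% of the planned enrollment". The chosen model will therefore be fitted four times.

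**The concern.** The trial randomises within strata but does not say that it will analyse by them. Stratified blocks make the arms more alike on site, chronic opioid use and surgery type, so the treatment estimate already varies less from trial to trial. A regression without those terms leaves the between-stratum variation in the residual and reports a standard error that is too large. There is no bias and no excess of false positives. What is lost is the width of the reported interval for the ratio of geometric means, together with a little power.

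There is also a matter of specification. With no covariates named, the choice between an adjusted and an unadjusted model stays open through three interim looks and the final analysis. Naming the terms settles it before any outcome data are seen.

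The opioid text is silent on covariates and does not exclude them. The pain model is explicit, because it lists its fixed effects and the strata are not among them.

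**Working it through.** **Inputs from Section 3.G.** Ratio of geometric means 0.60, so the log difference is |ln 0.60| = 0.5108. CV 0.85, so the log-scale variance is ln(1 + 0.85²) = 0.544 and the SD is 0.7374. Planned size is 67 per group (201), with a maximum of 237. Power is 90%. Sidedness is not stated, and two-sided is assumed.

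**The plan's own figure.** n per group = 2(z₁₋α/₂ + z₀.₉₀)² × 0.544 / 0.5108². This gives 52 at α = 0.025, and 65 (66 by noncentral t) at α = 0.05/6, that is, three pairs in two periods. The second is within two patients of 67, although the text does not state that split. (Using the CV itself as the SD with α = 0.025 gives 69.) None of these calculations allows for covariates, so the planned power does not depend on adjustment.

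**Interval width.** The documents do not give the share of chronic users, their relative consumption or the share of open surgery. Assume that a fraction p of patients are chronic users who consume f times as much, and that half the operations are open with g-fold consumption:

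R² = [p(1−p)(ln f)² + 0.25(ln g)²] / 0.544, and excess interval width = 1/√(1−R²) − 1.

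| Assumption | R² | Unadjusted interval wider by |
|---|---|---|
| p = 0.05, f = 1.5 | 0.014 | 0.7% |
| p = 0.10, f = 1.5 | 0.027 | 1.4% |
| p = 0.10, f = 2 | 0.080 | 4.2% |
| p = 0.10, f = 2, g = 1.25 | 0.102 | 5.5% |
| p = 0.10, f = 3 | 0.200 | 11.8% |

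For example, for f = 2: 0.09 × 0.4805 / 0.544 = 0.080.

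**Simulation of one analysis.** 201 patients, three arms, random blocks of 3, 6 or 9 within site × chronic use × surgery type, marginal log variance held at 0.544, p = 0.10, 12,000 tests per cell. Power is at ratio 0.60 and α = 0.025. Size is for a nominal 0.05 test (Monte Carlo SE 0.002).

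| Sites | f | SE ratio, unadjusted : adjusted | Power, unadjusted v adjusted | Unadjusted size |
|---|---|---|---|---|
| 2 | 1.5 | 1.013 | 95.9 v 96.3% | 0.047 |
| 2 | 2 | 1.041 | 96.5 v 97.4% | 0.042 |
| 2 | 3 | 1.118 | 96.8 v 98.6% | 0.036 |
| 6 | 1.5 | 1.010 | 95.8 v 96.1% | 0.051 |
| 6 | 2 | 1.039 | 96.3 v 97.0% | 0.046 |
| 6 | 3 | 1.113 | 96.8 v 98.6% | 0.042 |

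Adjusted size stayed at 0.048-0.053. The power gain is 0.3 to 1.8 points. A noncentral-t calculation gives 0.5 to 2.7 points, but it ignores the balance that stratification already provides and so overstates the gain. At f = 1.5, conservatism cannot be told from noise.

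**A second simulation with a different set-up** (237 patients, four sites, 15% chronic users, 50% open, nominal 0.025) shows where the effect lies. At R² = 0.20 the true spread of the estimate was 0.106 unadjusted and 0.105 adjusted, while the mean model SE was 0.117 against 0.105. Unadjusted size was 0.0135 and adjusted size 0.0222.

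**Four looks** at 59, 119, 178 and 237 patients, one comparison, overall two-sided 0.05, gamma −4 efficacy boundary, without futility or Holm. Overall size was 0.035-0.050 unadjusted and 0.048-0.052 adjusted.

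**Cost if the strata predict nothing.** The unadjusted : adjusted SE ratio at looks 1 to 4 is 0.972, 0.991, 0.996 and 0.997 with six site terms, and 0.985, 0.995, 0.997 and 0.998 with three site groups. So adjusted SEs are 2.9% or 1.5% larger at the first look (1/0.972, 1/0.985) and about 0.3% or 0.2% larger at the last. At 201 patients with six sites, power is 95.6% adjusted against 95.9% unadjusted.

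**The case against.** The case against is that nothing in the plan is wrong. The unadjusted analysis is valid and holds its type I error. Its power at ratio 0.60 is already about 96% at α = 0.025, against a target of 90%. For the opioid outcomes the point rests on silence, since a linear regression can carry covariates. Stratified blocks already deliver most of the benefit to the estimate itself: with two-fold use and two sites, its empirical SD was 0.1245 unadjusted and 0.1233 adjusted. Every magnitude is assumed, and the largest needs three-fold consumption in 10% of patients. The pain model is the one place where the omission is explicit, and there the gain has not been quantified.

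All of this stands, and it limits the point to a suggestion. It does not remove it. If the estimate is already more precise than the model reports, the reported interval is wider than the data justify, and adjustment corrects that. The benefit of fixing one model for all looks does not depend on how prognostic the strata are.

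Three further limits should be kept in view. The random-intercept option for site was not simulated, and with few sites its variance may be poorly estimated. The optional baseline covariates were not evaluated. The log-rank test for sensation and the chi-square tests for side effects also ignore the strata, but they are outside this point.

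**Conclusion.** The point holds as a matter to consider. The stratification factors are not named in the three opioid regressions, and they are absent from the listed fixed effects of the pain model. Followed as written, the analysis is unbiased and keeps its planned power. Its intervals are wider than necessary by about 1% to 12% for chronic users consuming 1.5 to 3 times as much at 10% prevalence, and the power gain from adjustment at ratio 0.60 is about 0.3 to 1.8 points. These sizes rest on assumed prevalence, fold differences, surgery mix and number of sites, none of which the documents give. The textual gap is certain; its practical size is not.

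**What to change.** State in the SAP that the 0-24, 24-48 and 48-72 h opioid regressions and the pain mixed model include chronic opioid use, anticipated surgery type (both as recorded at randomisation) and site as main effects. Use the same model at every interim look and at the final analysis. Handle site in a way that cannot change between looks: either a site grouping fixed before the first look without sight of outcome data, or a random intercept for site throughout. With few sites, the fixed grouping is the safer choice.

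Optionally, add recorded preoperative opioid use to the opioid models and preoperative pain score to the pain model. Keep the sample size and the internal-pilot resizing in Section 3.G on the marginal CV.

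The cost is wording only. All the variables are already collected and the sample size does not change. The models spend two degrees of freedom plus the number of site groups minus one. The worst case is strata that predict nothing, for which the small loss in standard error is shown above; it is largest at the first look, and fewer site groups reduce it.
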